4.9.3 Incomplete date for anti-neoplastic therapies

Prior therapies

Start date:

The same rule which is applied to the imputation of AE/concomitant medication start date will be used with the exception that for scenario (B) will be replaced to be 'start date of study drug -1'.

End date:

Imputed date = min (start date of study drug, last day of the month), if day is missing;
Imputed date = min (start date of study drug, 31DEC), if month and day are missing.

If the end date is not missing and the imputed start date is after the end date, use the end date as the imputed start date.

If both the start date and the end date are imputed and if the imputed start date is after the imputed end date, use the imputed end date as the imputation for the start date.

Post therapies

Start date:

Imputed date = max (last date of study drug + 1, first day of the month), if day is missing;

Imputed date = max (last date of study drug + 1, 01JAN), if day and month are missing.

End date:

No imputation.

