Only tumor assessments performed before the start of any further antineoplastic therapies (i.e., any additional secondary antineoplastic therapy or anticancer surgery) will be considered in the assessment of BOR. If a patient receives any further antineoplastic therapy while on study, any subsequent tumor assessments will be excluded from the BOR determination. Further antineoplastic therapies will be identified via protocol deviations (deviation code: COMDxx for use of prohibited concomitant therapy including other anticancer therapy, where xx is a serial number, e.g. COMD01, COMD02) or from the data collected on the [Antineoplastic Therapy Since Discontinuation of Study Treatment] eCRF pages, as appropriate. Clinical deterioration will not be considered as documented disease progression.

For patients with BOR of UNK, the reason for having unknown status will be listed. The following reasons will be used:

- No valid post-baseline assessment
- All post-baseline assessments have overall response UNK
- New antineoplastic therapy started before first post-baseline assessment
- SD too early (≤6 weeks after start date of study drug)
- PD too late (>12 weeks after start date of study drug)

Special (and rare) cases where BOR is 'Unknown' due to both early SD and late PD will be classified as 'SD too early'.

Frequency counts and percentages of patients with each BOR will be reported along with ORR and DCR.

Disease control rate

Disease control rate (DCR) is defined as the proportion of patients with a best overall response of CR, PR or SD, as assessed per RECIST 1.1 by the investigator.

DCR will be estimated and the exact 95% CI will be provided.

Time to response

Time to response (TTR) is defined as the time from the start date of study drug to the date of first documented response (PR or CR, which must be confirmed subsequently) for patients with a confirmed response (PR or CR) as assessed per RECIST 1.1 by the investigator.

TTR will be summarized using descriptive statistics for patients with a confirmed response (PR or CR). In addition, TTR will be summarized in 2-month intervals.

Duration of response

Duration of response (DOR) is defined as the time from the date of first documented response (PR or CR) to the date of first documented disease progression (PD) or death due to any cause among patients with a confirmed response (PR or CR) as assessed per RECIST 1.1 by the investigator.

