If a patient has not progressed or is not known to have died at the date of analysis cut-off or has received any further anticancer therapy in the absence of disease progression, DOR will be censored at the date of last adequate tumor assessment before the earlier of the cut-off date or the start date of new anticancer therapy. Clinical deterioration will not be considered as a qualifying event for progression. The censoring and event date options to be considered for the main analysis are presented in [Table 2-2](#).

Table 2-2 Outcome and event dates for DOR and PFS analyses

	Situation	Date	Outcome
A	No baseline assessment	Date of first dose of study drug [a]	Censored
B	Progression at or before next scheduled assessment	Date of progression	Progressed
C1	Progression or death after exactly one missing assessment	Date of progression (or death)	Progressed
C2	Progression or death after two or more missing assessments	Date of last adequate assessment	Censored
D	No progression	Date of last adequate assessment	Censored
E	Treatment discontinuation due to 'Disease progression' without documented progression, i.e. clinical progression based on investigator claim	N/A	Information ignored. Outcome derived based on radiology data only.
F	New anticancer therapy given	Date of last adequate assessment	Censored

Situation	Date	Outcome
[a] The rare exception to this is if the patient dies no later than the time of the second scheduled assessment as defined in the protocol in which case this is a PFS event at the date of death.		DOR will be described in tabular and graphical format using Kaplan-Meier methods. The Kaplan-Meier estimate of the distribution function will be constructed. The number of patients at risk at certain time points will be shown on the plot. The estimated median (in months) along with 95% CIs, as well as 25 th and 75 th percentiles, will be reported. (Brookmeyer and Crowley, 1982; Klein and Moeschberger, 1997). In addition, Kaplan-Meier estimated probabilities with corresponding 95% CIs (Kalbfleisch and Prentice, 2002) at several time points (including at least 4, 8, 12, 15, 18 months) will be summarized.

Refer to [Section 4.7.4](#) for further details regarding derivation of Kaplan-Meier estimates.

Progression-free survival

Progression-free survival (PFS) is defined as the time from the start date of study drug to the date of first documented disease progression (PD) or death due to any cause.

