If a patient has not progressed or is not known to have died at the date of analysis cut-off or has received any further anticancer therapy in the absence of disease progression, PFS will be censored at the date of last adequate tumor assessment before the earlier of the cut-off date or the start date of new anticancer therapy. Clinical deterioration will not be considered as a qualifying event for progression. Refer to [Table 2-2](#) for censoring and event date options and outcomes for PFS.

In particular, PFS will be censored at the last adequate tumor assessment if one of the following occurs: absence of event; the event occurred after a new anticancer therapy is given; the event occurred after two or more missing tumor assessments (see [Section 4.7.1](#)). See also [Section 4.6.1](#) describing the special case of a missing baseline tumor assessment.

PFS will be described in tabular and graphical format using Kaplan-Meier methods as described for DOR, including estimated median (in months) with 95% CI, 25th and 75th percentiles with 95% CIs, and Kaplan-Meier estimated probabilities with corresponding 95% CIs at several time points (including at least 4, 8, 12, 15 and 18 months). Censoring reasons will also be summarized.

In addition, the supportive analysis of PFS with censoring rule modified by ignoring further anticancer therapy ('F' in [Table 2-2](#)) will be considered when the percentage of patients censored due to the initiation of new anticancer therapy in the main analysis (for censoring reason classification, see [Section 4.7.1](#)) is equal to or more than 25% of the FAS (i.e., ≥ 5 out of 20 patients). In this supportive analysis, data from tumor assessments performed after the start of further anticancer therapy will also contribute to the determination of censoring and event date for PFS. Except for further anticancer therapy, the same censoring rule used for the main analysis will be followed. PFS will be described in a similar way, as needed.

Overall survival

Overall survival (OS) is defined as the time from the start date of study drug to the date of death due to any cause. If a patient is alive at the date of the analysis cut-off or lost to follow-

up, OS will be censored at the last contact date prior to the cut-off date (see [Section 4.3](#) for further details on derivation of last contact date).

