4.9.4 Incomplete assessment dates for tumor assessment

All investigation dates (e.g., X-ray, CT scan) must be completed with day, month and year.

If one or more investigation dates are incomplete but other investigation dates are available, the incomplete date(s) are not considered for calculation of the assessment date and assessment date is calculated as the latest of all investigation dates (e.g., X-ray, CT-scan) if the overall lesion response at that assessment is CR/PR/SD/UNK. Otherwise, if overall lesion response is PD, the assessment date is calculated as the earliest date of all investigation dates at that evaluation number. If all measurement dates have no day recorded, the 1st of the month is used.

If the month is not completed, for any of the investigations, the respective assessment will be considered to be at the date which is exactly between the previous and the following assessment. If both a previous and following assessments are not available, this assessment will not be used for any calculations.

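### SAP 4.9.3 dates a partially recorded post-study anticancer therapy without looking at a documented progression, so in patients already off LDK378 at the progression scan a true PFS or DOR event can be censored

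*SAP*

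**What the plan says.** For therapies started after study drug, SAP 4.9.3 gives two rules: "Imputed date = max (last date of study drug + 1, first day of the month), if day is missing" and "Imputed date = max (last date of study drug + 1, 01JAN), if day and month are missing". Each yields the earliest date compatible with a start after the last LDK378 dose. Neither refers to a progression date.

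The imputed date is used in three places in SAP 2.8.1:

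- PFS is censored at the last adequate tumor assessment when "the event occurred after a new anticancer therapy is given".
- DOR follows the same rule (Table 2-2, situation F): "DOR will be censored at the date of last adequate tumor assessment before the earlier of the cut-off date or the start date" of new therapy.
- Best overall response uses "Only tumor assessments performed before the start of any further antineoplastic therapies".

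Both the PFS and DOR texts, and protocol 10.5.2, apply this censoring to patients who take new therapy without having progressed. A documented progression followed by new therapy is meant to be an event.

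A supportive PFS analysis that ignores new therapy will be considered only if at least 25% of the FAS, 5 of 20 patients, are censored for that reason. The SAP describes no equivalent for DOR.

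**The concern.** Earliest-day imputation looks cautious, but here the imputed date decides whether a recorded progression counts. When the true order is last dose, progression, new therapy, the rule can reverse the last two. The patient then leaves the event count and is censored at the previous adequate scan.

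The protocol creates the setting. Patients who stop LDK378 without progression continue 8-weekly scans until progression (protocol 4.1 and 7.1.5.2), so progression can fall well after the last dose. Later therapies are collected at 12-weekly survival contacts, which may be by telephone (protocol 7.1.5.3), so a date without its day is plausible.

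At stake are PFS and DOR, DOR being a key secondary endpoint. The error moves events to censored, never the reverse. In a trial of about 20 patients with few responders, one misclassified event can show.

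**Working it through.** **1. The plan's own figure.** The trigger for the supportive PFS analysis is 0.25 × 20 = 5 patients, as the SAP states. Four flipped events would be 4/20 = 20% and would not reach it. The SAP gives no figure for partial therapy dates.

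**2. The rule applied to dates.** Imputed start = max(last dose + 1, first of month), or max(last dose + 1, 01 January) if the month is also missing. All dates are illustrative.

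| Situation | Last dose | PD | True start | Missing | Imputed start | PD in PFS/DOR |
|---|---|---|---|---|---|---|
| Off-treatment follow-up | 15 Mar | 20 Jun | 26 Jun | day | 1 Jun | censored |
| Off-treatment follow-up | 10 Feb | 14 Mar | 27 Mar | day | 1 Mar | censored |
| Scan 4 days after last dose | 10 Mar | 14 Mar | 27 Mar | day | 11 Mar | censored |
| Dosed through PD | 16 Mar | 14 Mar | 27 Mar | day | 17 Mar | counted |
| PD in the month before | 10 Feb | 25 Feb | 10 Mar | day | 1 Mar | counted |
| PD in the month before | 10 Feb | 25 Feb | 10 Mar | day and month | 11 Feb | censored |

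In the first row, a scan 56 days earlier falls on 25 April, and PFS is censored there.

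**3. Ties.** SAP 4.9.4 dates a progression to the earliest scan date of the evaluation, and adds: "If all measurement dates have no day recorded, the 1st of the month is used". If progression and therapy both lack a day, both can land on the first of the month. The SAP has no tie rule.

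**4. How often the order reverses, given a partial date.** The true order is last dose < PD < therapy. The gaps are assumed, with calendar dates drawn at random.

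| PD after last dose | Therapy after PD | Day missing | Day and month missing |
|---|---|---|---|
| 1–7 days | 1–7 / 8–14 / 15–28 days | 72% / 52% / 22% | 84% / 83% / 81% |
| 8–56 days | 1–7 / 8–14 / 15–28 days | 84% / 61% / 26% | 99% / 97% / 94% |
| Last dose on or after PD | any of these | 0% | 0% |

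**5. Direction.** Suppose n patients are at risk at time t, with the flipped event and j others. The Kaplan-Meier factor changes from (n − 1 − j)/n to (n − 1 − j)/(n − 1), which is larger. Between the earlier censoring time and t the curve is slightly lower. The upward bias therefore applies from t onward.

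**6. Size for PFS.** Assumptions: N = 20; exponential PFS with median 6.93 months (protocol Table 1-4, prior ALK inhibitor); scans exactly every 8 weeks; follow-up uniform over 6–24 months; k randomly chosen events censored one scan earlier; 4,000 trials.

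- k = 1: mean ratio of medians 1.11, median ratio 1.00, Kaplan-Meier median unchanged in about 70% of trials.
- k = 2 and 3: mean ratios about 1.2 and 1.3.

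With scans spread ±7 days and 18 months of follow-up, one flip raises the median in 62% of runs, but usually by days. The typical median goes from 7.4 to 7.5 months, and 8-month PFS from about 48% to 50%. With k = 2 the typical median is 9.0.

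**7. Size for DOR.** Assumptions: 6 responders (the plan's 30% illustration), exponential DOR with median 8.25 months (protocol Table 1-3), ±7-day scans and 18 months of follow-up. The typical median goes from 7.4 to 9.4 months with one flip and to 14.6 with two.

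**The case against.** Much of the opposing case stands.

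- **The path is narrow.** Treatment normally runs to progression and may continue beyond it, so the last-dose floor protects the usual patient. A flip needs LDK378 ended before the scan, a partial therapy date, and progression first within the same unresolved month or year. The AE discontinuation rate quoted in protocol 1.2.1.2.1 is 10.2%, or 0.102 × 20 ≈ 2 patients, before the other conditions apply. Other reasons for stopping would add some.
- **Partial dates may be resolved.** Protocol 9.4 provides for queries on missing values generally. Efficacy data, later therapies and PFS censoring reasons are all reported, so a careful reader could spot a flip. But the imputation rule exists for dates that remain partial, and the listings do not correct the estimate.
- **The supportive PFS analysis restores these events.** It does so only from 5 patients upward, and only for PFS.
- **Any alternative errs the other way** if therapy truly preceded progression. This is the strongest point where the month is missing. With a last dose in January and progression in November, assuming progression came first could credit up to ten months on another drug to LDK378.

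A reader might also infer that months of valid scans are lost from best overall response and that the primary ORR is distorted. The documents do not support that. Protocol Appendix 2 (15.1.17), on which the SAP relies for endpoint derivation, by default already excludes scans more than 30 days after the last dose. At an 8-week interval that leaves about one scheduled scan exposed, and losing a scan can only lower ORR.

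**Conclusion.** The point holds for PFS and DOR. The rule can turn a documented progression into a censored observation, contrary to the plan's own restriction of this censoring to patients who have not progressed, and the bias is upward. It applies to patients whose last dose preceded the progression scan: those in off-treatment tumor follow-up, or on a hold from which dosing never resumed. A reader might infer that any hold at the scan is enough, but if dosing later resumed, the last dose falls after progression and the event is kept.

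The number affected cannot be derived from the documents and is probably small. The 11% average rise in median PFS for one flipped event should not be read as the expected effect. It averages no change in about 70% of trials with jumps along the scan grid, the number of flips is assumed, and events were chosen at random rather than among off-drug patients. DOR is more exposed because few responders contribute. Both endpoints are descriptive in a single arm and ORR is not inflated, so this is an inexpensive correction worth making, not a threat to the primary result.

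**What to change.** Amend SAP 4.9.3 for use in PFS and DOR:

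1. **Only the day missing, and a documented PD in that month after the last dose:** impute the therapy start as the later of last dose + 1 and PD date + 1, capped at month end. Count a PD on the same day as the imputed start as an event. Otherwise keep the present day-missing rule.
2. **Day and month missing, and the order relative to PD cannot be determined:** report PFS and DOR under both bounds, once with the PD as an event and once with it censored.
3. **Listings:** flag imputed therapy dates in the efficacy listings.

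In the first two censored examples, step 1 gives starts of 21 June and 15 March, and the progressions of 20 June and 14 March count again.

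The cost is a short SAP amendment, a line of derivation code for step 1, and a second run of PFS and DOR if step 2 ever applies. No new data are needed. The downside of step 1 is that, if therapy really began before PD in that month, a PD is counted that the plan would censor. The discrepancy in therapy timing is then under a month.

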4.9.4 Incomplete assessment dates for tumor assessment

All investigation dates (e.g., X-ray, CT scan) must be completed with day, month and year.

If one or more investigation dates are incomplete but other investigation dates are available, the incomplete date(s) are not considered for calculation of the assessment date and assessment date is calculated as the latest of all investigation dates (e.g., X-ray, CT-scan) if the overall lesion response at that assessment is CR/PR/SD/UNK. Otherwise, if overall lesion response is PD, the assessment date is calculated as the earliest date of all investigation dates at that evaluation number. If all measurement dates have no day recorded, the 1st of the month is used.

If the month is not completed, for any of the investigations, the respective assessment will be considered to be at the date which is exactly between the previous and the following assessment. If both a previous and following assessments are not available, this assessment will not be used for any calculations.

4.9.5 Incomplete date for death or last contact

All dates must be completed with day, month and year.

If the day or month is missing, death will be imputed to the maximum of the full (non-imputed) last contact date (excluding the date of death) and the following:

- Missing day: 15th day of the month and year of death
- Missing day and month: July 1st of the year of death

If the day is missing from the date of last contact, it will be imputed to the 15th day of the month and year of last contact only if derived from the survival page.

4.9.6 Incomplete date for disease progression on alectinib prior to the start of study drug.

If day of progression associated with the [Prior Antineoplastic Therapy – Alectinib] eCRF page is missing then the imputed PD date is:

= min (midpoint between the end date of the prior alectinib medication and the end of the month, start date of LDK), if end date of prior alectinib medication is in the same month as the PD date.

= min (15th of the month of the PD date, start date of LDK), if end date of prior alectinib medication is in a month prior to the PD date.

= 15th of the month of the PD date, if end date of alectinib medication is in a month after the PD date.

If both day and month of progression associated with the [Prior Antineoplastic Therapy – Alectinib] eCRF page is missing then the imputed PD date is:

= min (midpoint between the end date of the prior alectinib medication and the end of the year, start date of LDK), if end date of prior alectinib medication is in same year as the PD date.

= min (July 1 of the year of the PD date, start date of LDK), if end date of prior alectinib medication is in a year prior to the PD date.

= July 1 of the year of the PD date, if end date of prior alectinib medication is in a year after the PD date.

Completely missing PD dates will not be imputed. For the midpoint calculation, if odd days in between (e.g., last dose of alectinib is 27 June 2012, and end of the month is 30 June 2012), then use the next day from the midpoint calculation (e.g., midpoint is 29 June 2013).

4.9.7 Incomplete date for last dose of study drug

Scenario 1

If the last date of study drug is after the analysis cut-off date or is completely missing and there is no [End of Treatment Phase Disposition] eCRF page and no death date, the patient should be considered to be on-going and use the cut-off date for the analysis as the last dosing date.

Scenario 2

If the last date of study drug is completely or partially missing and there is EITHER an [End of Treatment Phase Disposition] eCRF page OR a death date available then imputed last dose date:

= 31DECYYYY, if only Year is available and Year < Year of min (EOT visit date, death date).

= Last day of the month, if both Year and Month are available and Year = Year of min (EOT visit date, death date) and Month < the month of min (EOT visit date, death date)

= min (EOT visit date, death date), for all other cases

The imputed date will be compared with start date of study drug. If the imputed date < start date of study drug, then last date of study drug is set to start date of study drug; otherwise, use the imputed date.

5 Reference:

Brookmeyer R and Crowley J (1982). A Confidence Interval for the Median Survival Time, *Biometrics* 38, 29 - 41.

Clopper CJ and Pearson ES (1934). The use of confidence or fiducial limits illustrated in the case of the binomial. *Biometrika*; 26, 404-413.

Collet D (1994). Modelling survival data in medical research. London, Chapman & Hall.

FDA (2007). Guidance for Industry Clinical Trial Endpoints for the Approval of Cancer Drugs and Biologics, US Department of Health and Human Services.

Kalbfleisch JD and Prentice RL (2002). The Statistical Analysis of Failure Time Data. Wiley Series in Probability and Statistics.

Klein JP and Moeschberger ML (1997). Survival analysis: Techniques for censored and truncated data. New York, Springer.

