4.1.2.2 End of Treatment (EOT)

When the patient discontinues from study treatment, End of Treatment (EOT) visit must be performed as soon as possible and within 7 days of the last dose of LDK378. Patients will be contacted for the safety follow-up 30 days after their last dose of LDK378 to determine if they have experienced any new AEs and/or to follow resolution of ongoing AEs.

Following the cessation of tumor follow-up assessments, patients will be contacted every 3 months to assess patient survival status and/or whether the patient started any other antineoplastic therapies since discontinuing study treatment. Patients do not need to visit the clinic during the survival follow-up.

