2.6 Treatments (study drug, concomitant therapies, compliance)

The Safety Set will be used for all medication data summaries and listings unless otherwise specified.

Study drug and study treatment

Study drug and study treatment both refer to LDK378 and will be used interchangeably.

Date of first/last administration of study drug

The date of first administration of study drug is defined as the first date when a non-zero dose of study drug was administered and recorded on the [Dosage Administration Record (DAR)] eCRF page. For the sake of simplicity, the date of first administration of study drug will also be referred to as start date of study drug.

The date of last administration of study drug is defined as the last date when a non-zero dose of study drug was administered and recorded on the DAR eCRF page. This date will also be referred to as last date of study drug.

Study day

The study day for all assessments (e.g., tumor assessment, death, disease progression, tumor response, performance status, adverse event onset, laboratory abnormality occurrence, vital sign measurement, and dose interruption) will be calculated using the start date of study drug as the origin. For assessments occurring after or on the start date of study drug, study day will be calculated as:

Study day = Event date – Start date of study drug + 1.

The first day of study drug is therefore study day 1.

For any assessment or events such as baseline disease characteristics or medical history (e.g., time since diagnosis of disease) occurring prior to the start of the study drug, study day will be negative and will be calculated as:

Study day = Event date – Start date of study drug.

The study day will be displayed in the relevant data listings.

Dose exposure and intensity

Definitions of study drug exposure variables, as well as intermediate calculations, are provided in [Table 2-1](#).

Table 2-1 Study drug exposure variables

Variable	Definition
Duration of exposure (days):	Last date of study drug – Start date of study drug + 1 (Periods of interruption are not excluded.)
Cumulative dose (mg):	Total dose of study drug taken by a patient in the study
Number of dosing days (days):	Duration of exposure (days) – Number of zero dose days
% of actual days dosed (%):	$100 \times \text{Number of dosing days} / \text{Duration of exposure (days)}$
% of days received full dose (%):	$100 \times \text{Number of days received full (planned) dose} / \text{Duration of exposure (days)}$

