2.8.2 Safety

All safety analyses will be performed based on the Safety Set. All listings and tables will be presented for all patients, unless otherwise specified.

Baseline

Baseline is the result of an investigation describing the “true” uninfluenced state of the patient. The last available assessment before or on the start date of study drug is defined as “baseline” value or “baseline” assessment. If an assessment is planned to be performed prior to the first dose of study drug in the protocol and the assessment is performed on the same day as the first administration of study drug, it will be assumed that it was performed prior to study drug administration, if assessment time or first dose time is not collected or is missing. If assessment time and first dose time are collected, the observed time point will be used to determine pre-dose on study day 1 for baseline calculation. Unscheduled assessments before the start date of study drug will be used in the determination of baseline. See [Section 4.8.2](#) for further details on derivation of baseline for laboratory data and ECGs.

Patients who start study treatment and discontinue from the study on the same day may have 2 different sets of data collected on study day 1, one being reported to the cycle 1 day 1 visit, the other reported to the end of treatment (EOT) visit. Data reported at the EOT visit are not eligible for baseline selection.

Grouping for the analyses

The overall observation period will be divided into three mutually exclusive segments:

- Pre-treatment period: from day of patient’s informed consent to the day before first dose of study drug.
- On-treatment period: from day of first dose of study drug to 30 days after last dose of study drug (Note: for ongoing patients, from day of first dose of study drug to the data cut-off date).
- Post-treatment period: starting at day 31 after last dose of study drug.

The safety summary tables will include only assessments collected during the on-treatment period, i.e., assessments collected no later than 30 days after last dose of study drug and assessments collected before or on the data cut-off date for ongoing patients, unless otherwise specified.

For select items, shift tables or change from baseline summaries generated for laboratory, ECG, vital signs and change score generation may use data from pre-treatment period for baseline calculations.

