Partial AE start date	Treatment start date	Relationship	Imputation calculation	Imputed date
12mmmyyy	20OCT2001	Uncertain	NC	<blank>
ddmmm2000	20OCT2001	Before	(D)	01JUL2000
ddmmm2002	20OCT2001	After	(E)	01JAN2002
ddmmm2001	20OCT2001	Uncertain	(B)	21OCT2001
ddSEP2001	20OCT2001	Before	(C)	15SEP2001
ddOCT2001	20OCT2001	Uncertain	(B)	21OCT2001
ddNOV2001	20OCT2001	After	(A)	01NOV2001

4.9.2 Incomplete dates of initial diagnosis, first recurrence/progression and most recent relapse/progression

Missing day is defaulted to the 15th of the month and missing month and day is defaulted to 01-Jan.

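### SAP 4.9.7 moves a last dose with a known month in an earlier calendar year to the EOT or death date; SAP 4.9.2 can, as a lesser matter, date a pre-study progression up to 14 days after first dose

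*SAP*

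**What the plan says.** **Last dose (SAP 4.9.7, Scenario 2).** This applies when the last-dose date is partly or wholly missing and there is an end-of-treatment disposition page or a death date. It has three branches:

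1. Year only: "31DECYYYY, if only Year is available and Year < Year of min (EOT visit date, death date").
2. Year and month: "Last day of the month, if both Year and Month are available and Year = Year of min (EOT visit date, death date"), and the recorded month must also be earlier than the month of that minimum.
3. Default: "min (EOT visit date, death date), for all other cases".

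The only later check is a lower bound: "If the imputed date < start date of study drug, then last date of study drug is set to start date of study drug". Nothing compares the result with the recorded month or year.

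**Where the date is used.** SAP Table 2-1 defines duration of exposure as "Last date of study drug – Start date of study drug + 1" and divides cumulative dose by it to get dose intensity. SAP 2.8.2 sets the safety window: "On-treatment period: from day of first dose of study drug to 30 days after last dose of study drug". Protocol 4.1.2.2 requires the EOT visit "as soon as possible and within 7 days of the last dose of LDK378".

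**Progression before study entry (SAP 4.9.2).** For initial diagnosis, first recurrence and most recent relapse or progression: "Missing day is defaulted to the 15th of the month and missing month and day is defaulted to 01-Jan". No cap at first dose is given. SAP 4.9.6, for progression on alectinib, takes the minimum of the imputed date and the start of LDK378 in the branches where the result could otherwise fall after first dose.

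**The concern.** In 4.9.7 the month-end branch compares year and month separately. It needs the same year and a lower month number, whereas the intended test must be whether the recorded year-month precedes that of EOT or death. A record of DEC2016 with EOT in January 2017 fails the year test and drops to the default. A less complete record (2016 only) gives 31DEC2016, so knowing the month produces a date that contradicts the record. That cannot be the purpose of the rule.

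At stake for an affected patient are duration of exposure, dose intensity and relative dose intensity, and the cut-off deciding which AEs, laboratory values, ECGs and vital signs enter the summary tables. Where a later therapy also has a partial start date, SAP 4.9.3 imputes it from last dose plus 1 day, so the error carries over.

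In 4.9.2, the missing cap allows a negative time from most recent progression to first dose, a baseline item listed in SAP 2.3.

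**Working it through.** The plan states no figure for this point. The check applies the rules literally to constructed dates, which are not trial data.

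**1. Branches of 4.9.7 (day missing unless noted)**

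| Recorded last dose | EOT or death | Branch | Imputed | Days past end of recorded period |
|---|---|---|---|---|
| NOV2016 | EOT 05DEC2016 | month end | 30NOV2016 | 0 |
| 2016 only | EOT 05JAN2017 | year only | 31DEC2016 | 0 |
| DEC2016 | EOT 05JAN2017 | default | 05JAN2017 | 5 |
| NOV2016 | EOT 05JAN2017 | default | 05JAN2017 | 31 + 5 = 36 |
| NOV2016 | EOT 10JAN2017 | default | 10JAN2017 | 31 + 10 = 41 |
| DEC2016 | death only, 20MAR2017 | default | 20MAR2017 | 31 + 28 + 20 = 79 |

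**2. Size when EOT is on schedule.** Take every last-dose day from 01APR2016 to 31MAR2018 (730 days) with EOT 0 to 7 days later: 730 × 8 = 5,840 cases. The imputed date leaves the recorded month in 56. All 56 cross a year end: for each of two year ends, last doses on 25 to 31 December contribute 1 + 2 + … + 7 = 28. The largest overshoot is 7 days (last dose 31 December, EOT 7 January). None arise within one calendar year. The 56 shows where the rule fails; it is not an expected rate.

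In every affected case the true last dose is on or before the recorded month end, and the month end is before EOT or death. Month end is therefore always closer to the truth than the default.

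**3. Effect on exposure and the safety window.** First dose is 03OCT2016 and EOT 04JAN2017. I assume 750 mg every day to the true last dose and a cumulative dose not extended to the imputed date, so relative dose intensity (RDI) = true dosing days / duration of exposure.

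| True last dose | Quantity | True | Month end | SAP as written |
|---|---|---|---|---|
| 28DEC2016 (EOT on day 7) | exposure, days | 87 | 90 | 94 |
| | RDI | 100% | 87/90 = 96.7% | 87/94 = 92.6% |
| | window ends | 27JAN2017 | 30JAN2017 | 03FEB2017 |
| 28NOV2016 (EOT late) | exposure, days | 57 | 59 | 94 |
| | RDI | 100% | 57/59 = 96.6% | 57/94 = 60.6% |
| | window ends | 28DEC2016 | 30DEC2016 | 03FEB2017 |

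**4. SAP 4.9.2.** Time since progression = first dose minus imputed date, with a month of 30.4375 days (SAP 4.4).

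- First dose 06JUN2016, progression in June 2016 with day missing: 6 − 15 = −9 days, or −0.30 months.
- First dose on the 3rd: 3 − 15 = −12 days.
- Worst case, first dose on the 1st: 1 − 15 = −14 days, or −0.46 months.

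The 01-Jan default cannot fall after first dose when progression preceded first dose.

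**5. SAP 4.9.6 for comparison.** Over a grid with alectinib end and true progression both on or before first dose, 0 of 4,596,032 cases fell after first dose. The branches without a cap apply only when alectinib ended in a later month or year than the progression, so the imputed date precedes first dose anyway.

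**The case against.** **Protocol timing bounds the error.** With EOT within 7 days, the shift past month end is at most 7 days. This stands. A reader might take the 36-, 41- or 79-day cases as typical; the documents do not support that, since each needs a late EOT, a long interruption before discontinuation, or only a death date. Such cases can occur: SAP 2.6 defines last administration by the last non-zero dose, and Protocol 6.3.1 and 6.3.2 contemplate interruptions of more than 28 days.

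**Other controls come first.** Protocol 9.3 and 9.4 provide automatic checks and queries before lock, so an unresolved missing day should be uncommon. This also stands. It limits how often the rule is reached, not what the rule returns.

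**All safety data are listed with period flags (SAP 2.8.2).** True, and the window error can only over-include. The flag, however, uses the same last-dose date, so data in the extra days would lose the post-treatment flag.

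**Limb (b) is remote.** It needs first dose before the 15th, progression in that same month and an unrecorded day for an event at most 14 days old. A reader might infer from inclusion criterion 4a that patients often progress in the month they start. The criterion requires only that disease has progressed by enrollment and gives no interval, so that frequency has no source.

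**Conclusion.** Both rules are wrong as written, and neither document has text that closes either gap. The consequence is minor.

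- **(a) SAP 4.9.7.** A last dose with known year and month in a calendar year before that of min(EOT, death) is imputed outside its recorded month. On schedule the overshoot past month end is at most 7 days, and only at a year end. It lengthens exposure, lowers dose intensity (provided cumulative dose is not extended to the imputed date) and extends the on-treatment window for that patient.
- **(b) SAP 4.9.2.** The error is at most 14 days (0.46 months) in a descriptive baseline summary. No endpoint uses it.

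A reader might infer that the primary result is at risk. The ORR definition in SAP 2.7.1 does not use the last-dose date. The routes to response data are indirect: a later therapy with a partial start date (SAP 4.9.3), or Protocol Appendix 2's default of dropping assessments more than 30 days after last dose, if applied. Either would also need a decisive scan in the affected days.

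Nor is SAP 4.9.6 at fault on this point, assuming alectinib ended on or before first dose. Both cases are rare, and no frequency can be derived from the documents. In about 20 patients, though, one wrong record would be visible in the exposure and AE tables.

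**What to change.** **SAP 4.9.7, second branch.** Impute the last day of the recorded month whenever year and month are both recorded and that year-month is earlier than the year-month of min(EOT visit date, death date). DEC2016 with EOT 05JAN2017 then gives 31DEC2016, and NOV2016 with the same EOT gives 30NOV2016, 36 days earlier than now. Same-year results do not change.

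**SAP 4.9.2, most recent relapse/progression.** With day missing, use min(15th of the month, start date of study drug), as 4.9.6 does for progression on alectinib, and do not allow a date earlier than the diagnosis date. June 2016 with first dose 06JUN2016 then gives 06JUN2016, a time of 0 rather than −9 days.

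**Cost.** Two SAP lines and the matching program lines, made before database lock. No new data are needed, and no dose, visit or clinical rule changes.
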